#### 2.1.4 Monitoring

- The principal investigators will periodically monitor the trial progression to ensure aspects of the protocol are followed
- Study and source documentation will be reviewed for verification of data collected. Check the source documentation at visits
- Review the participants' study folders to ensure it is complete and current
- Create a tracking spreadsheet to keep track of participant activities, such as enrollment progress, phone numbers, WeChat account names, text message schedule for each participant, and NRT usage (Refer to document 11: tracking spreadsheet)
- Meeting with the study coordinator approximately once a week to review any issues found during screening, enrollment and any other study activities

## 2.2 RESEARCH ASSISTANT

### Step 1: Identifying Subjects, Screening and Eligibility, and Enrollment

- Recruitment will occur via physician referral and approaching individuals who are seeking care at the HIV clinic
- Individuals will be screened for eligibility (Refer to brief screening agreement)

### Step 2: Informed Consent Process

- RA must have enough copies of the consent documentation (Refer to document 2:adult informed consent form)
- The RA will conduct the consent process in a private location, hand out the printed consent form and review the form with the participant
- If the participant provides consent to participate, the adult informed consent form should be maintained in the participant's study file
- A copy of the signed consent document will be provided to the participant to keep
- RA will submit the signed participant informed consent forms to the study coordinator to be saved in the participant study file

Note: If a participant is withdrawn after enrollment, the consent form should still be maintained and not destroyed

- The study team obtaining the consent must also sign and date the consent form
- Record date the ICF has been signed on a tracking spreadsheet (Refer to document 11: tracking spreadsheet)
- The RA will record participant's contact information including WeChat name and telephone number (Refer to document 11: tracking spreadsheet)

### Step 3: Survey Administration and Randomization

- After participants sign the informed consent document, RA will administer the baseline survey, baseline demographics, smoking habits, and other information will be surveyed (Refer to document 3: baseline survey)
- For accurate baseline measurements, the protocol below will be followed:
  - The RA will conduct face-to-face baseline surveying process to all participants

- After participants complete the baseline survey, RA will make sure participant ID is written on the survey
  - Participant's identifiers are going to be removed from the survey and gets stored in another location separated from the survey answers. Survey responses are going to match participants' ID number in EpiData
  - The RA will enter the participant's ID and responses into EpiData
- The RA is going to conduct the randomization process after baseline surveys are completed. Corresponding participant ID and assigned group should be entered into EpiData

#### **Step 4: Intervention group (Counseling Sessions and Text Messages)**

- The RA will give each participant in the intervention group a self-help manual and 8-week dosage of NRT gum
- The text messages are going to be sent by the RA following the pre-determined schedule with pre-determined content (Refer to document 6: text messages)
- RA should keep a record of the messages that are sent and have not been sent to each participant (Refer to document 11: tracking spreadsheet)
- RA should keep a record of whether each participant is accepted the NRT gum (Refer to document 11: tracking spreadsheet)

#### **Step 5: Control group**

- The RA is going to give out a self-help manual and 8-week dosage of NRT gum to participants who are assigned to the control group
- RA should keep a record of whether each participant is accepted the NRT gum (Refer to document 11: tracking spreadsheet)

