### 2.1.2 Study visits

- **Pre-study visit procedures**
  - Prior to conducting study visits, the RA will ensure that appropriate materials are in place to help in the smooth running of the clinical research study activities. The materials needed to begin the trial is listed in Section 2.4. Below are the procedures needed to be done to begin the trial:
    - Train counselors according to the counseling guide to prepare for the counseling sessions

- Prepare the brief screening agreement, baseline survey, 8-week follow-up survey, and 12-week follow-up survey
- Prepare informed consent form (one form for the study participant to keep, one form to be collected by the RA)
- Set up EpiData system and be ready to enter participant data once the screening process starts
- Prepare approximately 110 envelopes for randomization
- Create a storage location to list participants' phone number
- Create a list to keep track of what messages have been sent to each participant
- Create a WeChat account for the study and for sending text messages
- The RA should be accustomed to accessing the WeChat account and sending the messages to each participant
- Print the self-help manual for each participant (110 copies)
- Purchase and prepare NRT gums to give out to participants (gums will be given out 8 week dosage at a time to all participants)
- Familiarize the usage instructions for the NRT gums to explain to participants
- Obtain usage instruction of the NRT gums to hand out to participants
- Training on using the CO monitor and filters (at least 100)
- **Study visit procedures**
  - The RA will conduct face-to-face interviews with potential participants and ask the screening questions (Refer to document 1: brief screening agreement)
    - If eligible: Make a note in tracking system that an individual was screened and was eligible, and the criteria for which they were eligible. Answers will not be retained.
    - If not eligible: Make a note in tracking system that an individual was screened and was ineligible, and note the criteria for which they were ineligible. Answers will not be retained.
  - The RA will collect and verify all signed informed consent documents and place them in participants' study folders (labeled by ID number).
  - Participants will receive a signed copy of the informed consent form
  - The RA will add participants' WeChat contact after participants have signed the informed consent form and are randomized into the intervention group

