### 2.1.3 Randomization

- Study statistician will produce a randomization scheme that is unknown to the RAs and produce 110 envelopes for randomization. Half of the envelopes indicate that participants are assigned to the control group, half of the envelopes indicate that participants are assigned to the intervention group
- After the completion of baseline questionnaire, RA is going to randomly open up an envelope to assign participants to either the control or the intervention group

- The RA is going to input participants' ID number and their assigned group into the data storage system (EpiData)

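### The gum and manual common to both arms are offered after the envelope is opened, so gum acceptance can be influenced by knowledge of the arm; the effect is probably small and cheap to avoid

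*Combined protocol and SAP*

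**What the plan says.** In the combined protocol and SAP, section 2.1.3 (Randomization) states: "After the completion of baseline questionnaire, RA is going to randomly open up an envelope to assign participants". The same RA then enters the participant's ID and group in EpiData. Section 2.2 (Research Assistant), Step 3, gives the same order: "The RA is going to conduct the randomization process after baseline surveys are completed".

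The background treatment comes in the next two steps, which are split by arm. Step 4: "The RA will give each participant in the intervention group a self-help manual and 8-week dosage of NRT gum". Step 5 has the RA hand over the manual and an "8-week dosage of NRT gum to participants who are assigned to the control group". Both steps also tell the RA to log whether the participant took the gum.

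Section 2.1.2 (Study visits) confirms that the supply is meant to be common: "gums will be given out 8 week dosage at a time to all participants". Among the RA's preparations it lists "Familiarize the usage instructions for the NRT gums to explain to participants", together with obtaining a printed usage instruction for participants. It does not say when the explanation is given.

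Section 2.4 (Statistical Analysis) regresses each abstinence outcome on treatment group, unadjusted and then adjusted. It mentions neither gum acceptance nor gum use.

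**The concern.** The trial is built to isolate counseling and text messages on top of a common base of manual and gum. That contrast is clean only if the base is delivered alike. Here a cessation aid that participants can refuse is offered by someone who has just learned the arm, and probably to someone who has just learned it too. A participant's reaction to the allocation, or the way the RA presents the gum, could shift acceptance in one arm. Any resulting difference in quitting would be counted in the treatment-group coefficient and read as an effect of counseling and texts.

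**Working it through.** **Order of events**

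1. Baseline survey (Step 3).
2. The RA opens the envelope and records the arm (section 2.1.3; Step 3).
3. The RA gives manual and gum and records acceptance (Step 4 or Step 5, by arm).

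Nothing in the documents puts the offer before allocation, keeps the person making it unaware of the arm, or scripts the spoken explanation. Section 2.1.1 has the RA prepare a manual and gum for every participant before launch, but that is stock preparation, not hand-out.

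**Size**

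The plan gives no quit rate, acceptance rate or gum effect, so there is no stated figure to reproduce. The only usable input is 110 envelopes split in half: 110 / 2 = 55 per arm. All other inputs are assumptions.

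Spurious difference = acceptance gap × gum benefit.

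- Low: 0.05 × 3 points = 0.15 points.
- High: 0.20 × 6 points = 1.2 points.

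Against sampling error, with an assumed quit rate p in both arms, SE = √(2p(1−p)/55).

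- p = 10%: √(0.18/55) = 5.7 points, so 1.2 points is 1.2/5.7 = 0.21 SE.
- p = 20%: √(0.32/55) = 7.6 points, so 1.2 points is 1.2/7.6 = 0.16 SE.

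A shift of 0.21 SE raises the two-sided 5% error rate to about 5.5%; at the low end it stays at 5.0%. One participant is 1/55 = 1.8 points, so the high case is less than one quitter per arm (0.012 × 55 = 0.66).

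**Sensitivity to larger assumptions**

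Take a quit rate of 10% without gum, no true effect of counseling or texts, and quit rate per arm = 10% + gum benefit × acceptance.

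| Quit rate with gum | Acceptance, intervention vs control | Spurious difference | Odds ratio | Type I error |
|---|---|---|---|---|
| 15% | 90% vs 80% | 14.5 − 14.0 = 0.5 points | 1.04 | 5.1% |
| 20% | 90% vs 70% | 19.0 − 17.0 = 2.0 points | 1.15 | 5.8% |
| 25% | 90% vs 60% | 23.5 − 19.0 = 4.5 points | 1.31 | 8.9% |

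The table puts the lower acceptance in the control arm for illustration only; the sign reverses if the gap does. The last row needs a 15-point gum benefit and a 30-point acceptance gap together.

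**Would the acceptance record show it?**

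With 55 per arm, power to detect a difference in acceptance is 31% for 90% vs 80% and 75% for 90% vs 70%. A moderate gap could go undetected by a test.

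**The case against.** The plan is consistent on this point: everyone is to get the same materials, and giving study materials after allocation is common. There are partial safeguards. The usage instruction is printed and common, acceptance is logged in both arms, gum usage has its own tracking sheet, and the investigators monitor conduct. Differential refusal is conjecture. Benefit also comes from using gum over weeks rather than from taking it home, so the formula above, which treats acceptance as use, overstates what a change of order would remove. All of this stands. It limits the size of the point but leaves the exposure in place, because none of these safeguards acts on the offer itself.

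A reader might infer four stronger claims that the documents do not support.

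- **That a gap in acceptance could not be an effect of the intervention, because no counseling has yet been given.** The first session is not dated. The Counselor section places sessions at follow-up appointments but also has the counselor notified once consent is signed. Hand-out before counseling is the likely order, not a documented one.
- **That the bias favors the intervention.** Controls might decline more from disappointment, or accept more readily because gum and manual are the only aids they are given.
- **That the explanation certainly follows the envelope.** Its timing is inferred from the hand-out steps.
- **That the planned analysis wrongly adjusts for acceptance.** Section 2.4 proposes no such adjustment.

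**Conclusion.** The point holds as an avoidable exposure in the order of procedures. It is neither an error in the analysis nor evidence of bias. The documents establish that a refusable treatment common to both arms is offered, and its acceptance recorded, after the RA knows the arm. They do not establish that acceptance will differ, or in which direction.

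Under an assumed gum benefit of 3 to 6 points and an acceptance gap of 5 to 20 points, the spurious difference is 0.15 to 1.2 points, at most about 0.2 standard errors with 55 per arm. Larger distortions need assumptions for which the documents give no basis. The case for change therefore rests on its low cost more than on the likely size of the bias.

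**What to change.** In section 2.2 (Research Assistant), Step 3, after the baseline survey and before the envelope is opened, have the RA offer the same manual and gum to every participant, go through the printed usage instruction, and record acceptance. Then randomize. Delete the matching hand-out and acceptance bullets from Steps 4 and 5; Step 5 contains nothing else, so it would need a line pointing back to Step 3.

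The supply itself does not change, and no staff, product or visit is added. The cost is an occasional pack lost when someone leaves between the offer and the envelope. Acceptance then becomes a baseline variable.

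The change removes knowledge of allocation from the offer, the initial explanation and acceptance only. Gum use afterward may still differ by arm, whether through counseling and texts or because participants know their arm.

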#### **Step 6: Follow-up Visits**

- The RA is going to administer the follow-up survey at 8-week and 12-week (Refer to document 4: 8-week survey and document 5: 12-week survey)
- RA has the flexibility to administer the surveys over WeChat or phone if in-person administration is not possible
- The RA is going to make sure that surveys are completed by the participants and have participants' ID number on each survey
- The RA is going to enter ID numbers and responses into EpiData

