### User/audience

- Principal Investigators, Co-Investigators
- Counselor
- Research Assistants (RA)

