### 2.1.1 Pre-launching

- Before launching the study, the study research assistant will:
  - Approach individuals who attend the HIV clinic at GMU and conduct face-to-face interviews to screen them for eligibility.
  - Get notified by physicians at the clinic of potentially eligible/interested participants so that the RA can conduct face-to-face interviews to screen them for eligibility
  - Get trained on conducting follow-up counseling sessions according to the counseling guide
  - Prepare baseline and follow-up surveys in the same format across participants (via computer, WeChat, in-person etc.)
  - Ensure paper data forms are finalized and computer data entry systems are ready for data entry (EpiData) so that computer-generated spreadsheets of data can be generated
  - The RA will prepare self-help manual and NRT gum for every participant
  - Purchase the CO monitor, train users how to use it for biochemical verification of quitting at 12-month follow-up assessment
  - Train the counselor using the counseling guide that is established to conduct counseling sessions. Counselors should be familiar with the content and procedures of the guide to communicate with participants
  - Counselor should be familiar with referral services around the area/online for smoking cessation

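### One role, the RA, covers allocation, intervention messaging, follow-up surveys and CO recording with no separation, so self-reported abstinence is collected open to allocation

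*Combined protocol and SAP*

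**What the plan says.** Section 2.1.3 conceals the sequence in advance: "Study statistician will produce a randomization scheme that is unknown to the RAs". Concealment ends at allocation, when the "RA is going to randomly open up an envelope to assign participants to either the control or the intervention group". The RA then enters the assigned group in EpiData against the participant's ID.

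For the intervention arm, section 2.1.2 has the RA add the participant as a WeChat contact after randomization to that arm. Step 4 continues: "The text messages are going to be sent by the RA following the pre-determined schedule with pre-determined content". The RA logs those messages on the tracking spreadsheet and tells the counselor when a new intervention participant joins (section 2.2 Counselor, Step 1). Section 2.1.1 also lists among the RA's preparations: "Get trained on conducting follow-up counseling sessions according to the counseling guide".

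On outcomes, Step 6 says: "The RA is going to administer the follow-up survey at 8-week and 12-week". The RA may use WeChat or phone when an in-person survey is not possible. In Step 7 the RA learns the CO method and records the 12-week result in EpiData. Section 2.4 makes CO below 8 ppm at 12 weeks the primary outcome and 7-day point prevalence abstinence at 8 and 12 weeks a secondary outcome.

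The manual mentions no blinded assessor, no division of duties among RAs and no restriction on seeing the group field at follow-up.

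**The concern.** Self-reported abstinence depends on how the question is put and on who puts it. Under this manual, an intervention participant may be asked about smoking by the person who sent the quit messages, possibly on the same WeChat channel. A control participant has no such history with the interviewer. If that leads more continuing smokers to claim abstinence in the intervention arm than in control, the comparison shifts towards the intervention without any real effect. At 8 weeks there is no breath test to set against the answer.

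The CO outcome is open in a narrower way. Breath cannot be tested over WeChat or phone, and an RA who knows the arm judges when an in-person visit is not possible. Section 2.4 does not say how missing CO is handled, and the manual has no rule on repeat readings.

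**Working it through.** **Step 1. Who does what, and does that role know the arm?**

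| Task | Assigned to | Place | Arm known? |
|---|---|---|---|
| Open envelope, enter group in EpiData | RA | 2.1.3 | Yes |
| Add WeChat contact (intervention arm only) | RA | 2.1.2 | Yes |
| Send and log messages (intervention arm only) | RA | Step 4 | Yes |
| Tell counselor of new intervention participants | RA | 2.2 Counselor, Step 1 | Yes |
| 8- and 12-week surveys | RA | Step 6 | Not prevented |
| Record 12-week CO in EpiData | RA | Step 7 | Not prevented |

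Follow-up results go into the system that holds the assigned group. Even a second RA could therefore learn the arm, unless the group field and the message log stay closed.

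**Step 2. Which outcomes are exposed?**

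- 8-week abstinence: self-report only. Most exposed.
- 12-week abstinence: self-report, with a CO reading planned at the same time point.
- 12-week CO: instrument reading with a fixed cut-off. Least exposed. What remains open is the choice of remote follow-up and the recording of readings.

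**Step 3. Scale for self-report, by illustration.** The plan states no alpha, power, event rate or dropout, so it has no figure to reproduce. From section 2.1.3, 110 envelopes split equally give 110/2 = 55 per arm, and one participant is 100/55 = 1.8 percentage points. Everything else here is assumed: no true effect, complete follow-up, two-sided 5% test (2.5% in each direction), and a two-proportion test standing in for the unadjusted logistic model.

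Let q be true abstinence and f the share of continuing smokers who report abstinence. The observed rate is q + (1 − q)f. Take q = 0.15.

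*Case A, f = 0.05 intervention, 0 control:*
- Rates: 0.15 + 0.85 × 0.05 = 0.1925, against 0.15.
- Odds ratio: (0.1925/0.8075)/(0.15/0.85) = 1.35.
- SE: √[(0.1925 × 0.8075 + 0.15 × 0.85)/55] = 0.0717.
- Chance of significance favouring the intervention: Φ(0.0425/0.0717 − 1.96) = 8.6%.

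*Case B, f = 0.10 intervention, 0.05 control:*
- Rates: 0.235 against 0.1925.
- Odds ratio: (0.235/0.765)/(0.1925/0.8075) = 1.29.
- SE: √[(0.235 × 0.765 + 0.1925 × 0.8075)/55] = 0.0781.
- Chance: Φ(0.0425/0.0781 − 1.96) = 7.8%.

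**Step 4. Range.** Exact binomial enumeration of the pooled two-proportion test, 55 per arm, misreporting in the intervention arm only. Cells give the two-sided false-positive rate, with the spurious difference (1 − q)f in brackets.

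| True abstinence | f = 0 | f = 5% | f = 10% | f = 15% |
|---|---|---|---|---|
| 10% | 5.0% | 10.8% (4.5 points) | 26.5% (9.0) | 48.4% (13.5) |
| 20% | 5.1% | 8.1% (4.0) | 16.5% (8.0) | 29.9% (12.0) |
| 30% | 5.1% | 7.0% (3.5) | 12.6% (7.0) | 21.8% (10.5) |

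These tables show sensitivity. They do not say how much misreporting will occur, or how much of it comes from the assessor.

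**The case against.** Several points on the other side stand.

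- **Role and person.** Tasks are given to a role, and the manual refers to RAs in the plural. A reader might infer that one individual demonstrably does everything for each participant. The text does not show that; it only fails to prevent it.
- **Staffing.** A reader might also infer from the plural that existing staff can certainly be split. RA numbers, shifts and workload are not given, so this is plausible but unproven.
- **Contact.** Message content is fixed in advance and sent through a study account. The counselor, not the RA, delivers the sessions, and the RA's counseling training does not show otherwise. The RA also meets control participants at baseline and gives them the manual and gum. A close personal tie between interviewer and intervention participant is not established.
- **Self-completion.** Step 6 has the RA check that participants have completed the surveys, which may mean that they fill them in themselves. The survey forms were not supplied, so this is unsettled.
- **Participants' own knowledge.** Only one arm gets messages and counseling, so participants know their arm and may over-report to any assessor.
- **Primary outcome.** An instrument reading against a fixed cut-off gives an assessor little room.
- **Other document.** The manual supplements an IRB protocol that was not supplied and may specify blinded assessment.

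These points limit the size and reach of the concern. They do not supply the missing safeguard: the manual leaves open who collects outcomes and whether that person can see the arm.

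**Conclusion.** The point holds as a gap in the manual that is worth closing. Allocation, messaging, surveys and CO recording sit with one role and nothing separates them. The consequence falls mainly on the secondary outcome of 7-day abstinence, most of all at 8 weeks.

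A reader might go further and conclude that the primary result is biased, or that the false-positive rate is about 8% to 9%. The documents support neither. The rates concern self-report only, rest on assumed abstinence and misreporting and on all 55 per arm being followed up, and count all differential misreporting, including the part that blinding an assessor would leave. The share that the fix would remove is unknown. This is a recommended improvement, with medium confidence.

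**What to change.** Amend Steps 6 and 7 as follows.

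1. Participants complete the smoking questions themselves, on the same paper or computer form in both arms, with the RA checking only completeness. WeChat should not be the mode: WeChat names are collected at consent, but the contact is opened only for intervention participants, so the channel differs by arm and reveals it.
2. The 12-week CO reading is taken and recorded against the ID before smoking status is discussed.
3. Where more than one RA is available, follow-up is done by an RA who neither randomized nor messaged that participant. The EpiData group field and the message-tracking sheet are not opened at follow-up.
4. If the IRB protocol already specifies blinded assessment, reconcile the manual with it.

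The first two items need no second person. The cost is revised wording, a small change in data access and less flexible scheduling of follow-up. Some reporting bias will remain because participants know their arm.
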